9.2.4 Derivation of Other Variables

Age at initial OFC. Age will be calculated using the date of birth (DOB) and the date of the OFC, and presented as age at last birthday as an integer.

Timing of Study Visits (SVs) and Additional Study Visits (ASVs). The number of days from initial OFC and initial dose escalation visit will be calculated for each SV or ASV as the difference in the two dates (Date of SV/ASV – Date of OFC/initial dose escalation visit). (Refer to mock Table 1.4)

9.3 Demographic and Baseline Variables

Demographic data presented will be age at OFC, gender, ethnicity, and race. Baseline/enrollment variables presented will be height, weight, and known history of asthma, allergic rhinitis, and atopic dermatitis. Demographic data will be summarized in separate columns for the Intention to Treat, Efficacy, and Safety populations; if any of these represent the same population, the columns will be combined. (Refer to mock Table 1.3.)

9.4 Study Drug Administration

For each patient and each dose escalation visit, the maximum dose tolerated (mg) and dose to be taken at home (mg), as reported on the CRF for study drug administration, will be listed for the ITT population (all enrolled patients) in a single table. (Refer to mock Table 4.1.)

9.5 Treatment Compliance

Treatment compliance will be summarized separately for each SV and ASV using fields from the CRF for study drug compliance, including the number of patients with at least one missed dose and reasons for missed doses reported by at least one patient. The population for each SV table will be all patients in the corresponding Study Visit population. (Refer to mock Tables 4.2.1 -4.2.10.)

10 Efficacy Analyses

10.1 Analysis of Primary Efficacy Endpoint

The primary efficacy endpoint is 'response to treatment' defined as ability to successfully consume a single dose of 300 mg or greater of peanut protein with no dose limiting symptoms at the exit DBPCFC. The analysis population will be the Primary Endpoint ITT population. Subjects with missing data on the primary endpoint will be considered as non-responders for the primary analysis. Due to the small sample size, exact rather than asymptotic statistical methods will be used for the analysis of this endpoint.

The proportion of patients who respond to treatment will be assessed using a one-sample superiority analysis compared to an expected proportion of 20%. The null hypothesis is that the proportion of patients who respond to treatment is less than or equal to 20%, and the alternative hypothesis is that the proportion of patients who respond to treatment is greater than 20%.

As this is a proof-of-concept study, statistical significance in the analysis of primary efficacy endpoint will be assessed using a one-sided 0.05 level of significance (or two-sided 0.1) rather than a one-sided 0.025 level of significance (or two-sided 0.05). The alternative hypothesis of superiority will be accepted if the lower bound of the one-sided 95% Clopper-Pearson exact confidence interval (equivalent to the lower bound of a two-sided 90% confidence interval) for the primary efficacy endpoint is greater than 20%; the p-value for the exact binomial test at a one-sided significance level of 0.05 will also be provided. The summary statistics will be reported as described in section 9. (Refer to mock Table 2.1.)

10.2 Analysis of Secondary Efficacy Endpoints

Secondary efficacy endpoints consist of changes in continuous or ordinal variables from the

enrollment/baseline, initial OFC, or initial dose escalation visit to the final study visit. The primary analyses of the change endpoints will be performed using Wilcoxon signed rank tests, with null hypotheses of no change, versus two-sided alternative hypotheses at a significance criteria of 0.05. Missing data will not be imputed, and complete cases only will be analyzed (see section 8.4). Due to the small sample size, visual assessments of the symmetry assumptions of the Wilcoxon signed rank tests are unlikely to be definitive, and p-values for Sign tests under the same null hypotheses and significance criteria will also be presented as sensitivity analyses. The summary statistics will be reported as described in section 9.

Highest tolerated dose and cumulative tolerated dose. Changes in highest tolerated dose and cumulative tolerated dose from initial OFC to the peanut protein arm of the exit DBPCFC will be analyzed as ordinal variables, using nonparametric tests. The analysis population will be the Efficacy Population. (Refer to mock Table 2.3.)

Serum markers of sensitization and tolerance to peanut. Changes in serum markers of sensitization and tolerance to peanut will be analyzed as continuous variables using nonparametric tests. The analysis population will be the Modified Efficacy Population for immune response. (Refer to mock Table 2.4.)

FAQLQ. Changes in FAQLQ subscale and summary scores will be analyzed as continuous variables using nonparametric tests. The percent of patients with change in summary score greater than or equal to the MID will be reported with 95% Clopper-Pearson exact confidence interval. Hypothesis testing will be performed for summary scores only. Parent and Teenager forms will be analyzed separately, and the analysis populations will be the Modified Efficacy Populations for FAQLQ-PF and FAQLQ-TF. (Refer to mock Tables 2.5 and 2.6.)

11 Safety Analyses

Safety analyses will be performed on the safety population unless otherwise specified. Summary statistics will be reported as described in section 9.

11.1 Adverse Events

All AEs that affect at least one patient will be reported. AEs will be *categorized* as corresponding to a study phase (dose escalation study visit, home dose, exit DBPCFC, etc.), and reported within study phase and overall. They will be further *grouped* by preferred term, CoFAR severity grade, or treatment given. AEs that meet SAE criteria will also be categorized as corresponding to a study phase, and reported within study phase and overall. Adverse events data will be tabulated within the categories and groups described above at both the *patient* and *dose* level.

Patient-level analysis. The *number of patients* that experience the AE or SAE at least once will be tabulated. Within category and group, each subject will be counted once and any repetitions will be ignored.

Dose level analysis. The *number and percentage of study medication doses* in the category and group that are associated with the AE or SAE. The total number of doses of study medication will be reported for each category, and the denominator for the calculation of the percentages will be the total number of doses given by category.

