1.1 Study Synopsis

Title: Boiled Peanut Oral Immunotherapy

Study Description: Prospective Phase 1 clinical trial providing proof of concept data on boiled peanut oral immunotherapy (OIT) for the treatment of peanut allergy in children. We hypothesize that the proportion of subjects successfully desensitized with boiled peanut OIT is greater than the theoretical placebo rate of 20%.

Objectives:

- Determine the effect of boiled peanut immunotherapy on the immune response to peanut.
- Compare the safety and tolerability of boiled peanut oral immunotherapy to published data on roasted peanut oral immunotherapy in pediatric subjects with confirmed IgE mediated peanut allergy.
- Primary endpoint: Response to treatment defined as ability to successfully consume a single dose of 300 mg or greater of peanut protein with no dose limiting symptoms at exit double blind placebo controlled food challenge (DBPCFC).
- Secondary endpoints:
- Maximum dose achieved with no or minimal symptoms at exit DBPCFC.
- Change in the maximum tolerated dose from screening to exit DBPCFC.
- The rate of side effects of treatment defined as oral itching, rhinorrhea, conjunctivitis, urticaria, angioedema, abdominal upset, vomiting, diarrhea, cough, wheeze, or anaphylaxis.
- Change in quality of life scores before and after treatment utilizing validated, age specific, food-related quality-of-life surveys before and after peanut oral immunotherapy (Supplement 1)
- Peanut protein component panel, to determine the presence of high levels of sensitivity to peanut proteins known to be associated with severe systemic reactions (Arah 1,2,3) versus mild reactions (Arah8).

Endpoints:

- Levels of peanut specific serum IgG4, with higher levels associated with increased tolerance to peanut protein.

Study Population:

Children ages 1-16 with peanut allergy suggested via history of reaction and objective evidence of IgE mediated hypersensitivity either via skin testing or in vitro testing (peanut specific IgE concentration) within the last 12 months.

Inclusion criteria:

[figure not shown]
- Age 1-16 years
- History of immediate hypersensitivity reaction to peanut or a high level of suspicion based on testing at the discretion of the investigator
- Evidence of IgE mediated peanut hypersensitivity within a 12 month period of study enrollment including:
 - Skin prick test with wheal diameter of at least 3mm and/or
 - Peanut specific IgE >0.35 ku/L

Exclusion criteria:

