8.3.3.2 Relationship to Study Intervention

All adverse events (AEs) must have their relationship to study intervention assessed by the clinician who examines and evaluates the participant based on temporal relationship and his/her clinical judgment.

The degree of certainty about causality will be graded using the categories below. In a clinical trial, the study product must always be suspect.

- **Definitely Related** – There is clear evidence to suggest a causal relationship, and other possible contributing factors can be ruled out. The clinical event, including an abnormal laboratory test result, occurs in a plausible time relationship to study intervention administration and cannot be explained by concurrent disease or other drugs or chemicals. The response to withdrawal of the study intervention (dechallenge) should be clinically plausible. The event must be pharmacologically or phenomenologically definitive, with use of a satisfactory rechallenge procedure if necessary.
- **Probably Related** – There is evidence to suggest a causal relationship, and the influence of other factors is unlikely. The clinical event, including an abnormal laboratory test result, occurs within a reasonable time after administration of the study intervention, is unlikely to be attributed to concurrent disease or other drugs or chemicals, and follows a clinically reasonable response on withdrawal (dechallenge). Rechallenge information is not required to fulfill this definition.
- **Potentially Related** – There is some evidence to suggest a causal relationship (e.g., the event occurred within a reasonable time after administration of the trial medication). However, other factors may have contributed to the event (e.g., the participant's clinical condition, other concomitant events). Although an AE may rate only as "possibly related" soon after discovery, it can be flagged as requiring more information and later be upgraded to "probably related" or "definitely related", as appropriate.
- **Unlikely to be related** – A clinical event, including an abnormal laboratory test result, whose temporal relationship to study intervention administration makes a causal relationship improbable (e.g., the event did not occur within a reasonable time after administration of the study intervention) and in which other drugs or chemicals or underlying disease provides plausible explanations (e.g., the participant's clinical condition, other concomitant treatments).

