5.2 Endpoints

Primary Endpoints. Response to treatment defined as ability to successfully consume a single dose of 300 mg or greater of peanut protein with no dose limiting symptoms at exit double blind placebo controlled food challenge (DBPCFC).

The highest dose of roasted peanut protein tolerated by the subject at exit DBPCFC will also be compared to the highest dose tolerated at baseline.

The effect of boiled peanut immunotherapy on the immune response to peanut will be evaluated via specific serum markers of sensitization and tolerance to peanut.

- Levels of serum specific peanut IgE, with higher levels associated with greater likelihood of clinical reaction on exposure to peanut protein.

- Peanut protein component panel, to determine the presence of high levels of sensitivity to peanut proteins known to be associated with severe systemic reactions (Arah 1,2, 3) versus mild reactions (Arah8)
- Levels of peanut specific serum IgG4, with higher levels associated with increased tolerance to peanut protein

These markers will be evaluated at baseline and the conclusion of the study.

Secondary Endpoints. The rate of adverse events in the subjects receiving boiled peanut oral immunotherapy. Possible adverse events include: side effects of treatment defined as oral itching, rhinorrhea, conjunctivitis, urticaria, angioedema, abdominal upset, vomiting, diarrhea, cough, wheeze, or anaphylaxis

- Adverse events will be recorded in terms of the percentage of subjects with adverse events on initial escalation day and at dose escalation visits by CRU staff.
- Adverse events will also be recorded in terms of overall percentage of home doses that result in adverse reaction, with data compiled from home logs.

The adverse reactions will be graded in severity and the treatment required will be recorded.

Validated, age-specific, food-related quality-of-life surveys before and after peanut oral immunotherapy will be completed by all patients/families.

6 Study Methods

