11.1.2 Comparative AE table

AE data from this study will be compared descriptively to the AE data from three published studies: the study medication arms of the Phase 2 and Phase 3 trials of AR101 OIT for peanut allergy (Bird et al., 2018; Vickery et al. for PALISADE, 2018), and OIT data from the PACE meta-analysis study of OIT for peanut allergy (Chu et al., 2019). No hypothesis testing will be performed.

For this table, study AEs will be categorized into two study phases as best corresponds to the comparative data: 1) initial dose escalation study visit, and 2) an increasing dose phase which includes all other dose escalation study visits and home doses, but excludes the exit DBPCFC. AEs will be grouped into severity grades, treatments, and preferred terms, where the preferred term list will include the specific AEs of interest only (see sections 5.2 and 9.2.3). (Refer to mock Table 3.3 for comparative data and source information.)

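### The SAP text never uses the relatedness grade collected for every AE, so patient-level and comparative AE rows mix treatment reactions with ordinary childhood illness; related-AE rows should be added

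*SAP*

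**What the plan says.** **Endpoint.** It is worded in two ways. Protocol 1.1 lists as a secondary endpoint "The rate of side effects of treatment defined as oral itching, rhinorrhea, conjunctivitis, urticaria, angioedema, abdominal upset, vomiting, diarrhea, cough, wheeze, or anaphylaxis". Protocol 3 and SAP 5.2 start from the rate of adverse events in treated subjects and then bring in the same list: "Possible adverse events include: side effects of treatment defined as oral itching, rhinorrhea, conjunctivitis, urticaria, angioedema, abdominal upset, vomiting, diarrhea, cough, wheeze, or anaphylaxis". For home dosing, SAP 5.2 uses the "overall percentage of home doses that result in adverse reaction, with data compiled from home logs".

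**Collection.** Protocol 8.3.3.2 states: "All adverse events (AEs) must have their relationship to study intervention assessed by the clinician who examines and evaluates the participant". There are five categories, from definitely related to not related. Protocol 8.3.4 puts the relationship on the case report form and requires AEs to be documented whatever it is.

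**Analysis.** SAP 11.1 reports every AE that affects at least one patient, by study phase and overall, with SAEs also shown, at patient and dose level. Within that, AEs are grouped "by preferred term, CoFAR severity grade, or treatment given". For the comparison with published studies, SAP 11.1.2 says "AEs will be grouped into severity grades, treatments, and preferred terms", limited to the listed terms of interest.

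**The concern.** The objective asks what boiled peanut does to children, and the trial is single-arm (SAP 6.1), so no concurrent group shows how often the listed symptoms occur without treatment. Several of those terms are also symptoms of colds and gastroenteritis. The protocol expects such illness: Protocol 5.3 tells families to call about it, and Protocol 8.2 screens for it at visits. The one collected field that addresses attribution is not carried into any analysis described in the SAP text. At stake is whether the descriptive comparison with roasted-peanut OIT can be read as a comparison of treatment side effects.

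**Working it through.** **Plan's own figure.** The plan gives none for AE rates. Its one design figure, power above 90% with 10 children (SAP 7), concerns the primary endpoint. By the exact binomial, requiring at least 5 responders of 10 gives a one-sided error of 0.0328 at 20% and power of 0.9936 at 80%. The figure is reproduced, and nothing below depends on it.

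**Tracing relatedness through the SAP text.**
- SAP 6.3.3 and 9.2.3 classify AEs by severity, term, treatment required and phase. Relatedness is not a derived variable.
- SAP 11.1 and 11.1.1 (Tables 3.1, 3.2) use phase, SAE status, term, grade and treatment given. Events in both arms of the exit challenge, including the oat placebo arm, count towards the totals.
- SAP 11.1.2 (Table 3.3) filters by term, not by attribution.
- SAP 11.1.3, 11.2.2 and the list of tables in SAP 14 do not mention relatedness.

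Phase and SAE status are real splits, but neither says whether peanut caused the event. Protocol 2.2 shows why that matters: of the four AR101 patients with severe SAEs in the published phase 3 trial, two had events unrelated to treatment. With 10 children, one such event here is 1/10 = 10%.

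**Size of the background at patient level (assumed rates).** Let λ be unrelated episodes per child-month with any listed term, Poisson, over m months. The share of children with at least one episode is 1 − exp(−λm). For 18 weeks, m = 18 × 7 / 30.4375 = 4.14. For the 14 weeks from initial escalation to the seventh escalation visit, m = 14 × 7 / 30.4375 = 3.22.

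| λ (assumed) | 18 weeks | 14 weeks |
|---|---|---|
| 0.1 | 34% | 28% |
| 0.25 | 64% | 55% |
| 0.5 | 87% | 80% |
| 1.0 | 98% | 96% |

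These shares pool all listed terms. The tables have one row per term, so each row would carry less.

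**Dose level (upper bound).** Suppose every daily dose taken on a symptomatic day counts as associated with the AE. With d symptomatic days per episode, the background share of doses is λ × d / 30.4375. For d = 1 it runs from 0.1/30.4375 = 0.3% to 1.0/30.4375 = 3.3%. For d = 5 it runs from 1.6% to 16.4%. Published dose-level rates in Protocol Table 1 run from 0.8% to 46%.

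**The case against.** The strongest reply is that the SAP tabulates the endpoint as written. Protocol 3 and SAP 5.2 speak of the rate of adverse events, Protocol 8.3.1 defines an AE regardless of causality, and side effects are defined by a symptom list rather than by a causality grade. This stands. A reader might infer that all-cause counts are the wrong endpoint, and the documents do not support that.

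Nor does ordinary illness automatically count against a dose. The home log (Protocol 12.3) is tied to a dose, asks whether there was a reaction, and records onset after it. SAP 11.1 counts only doses associated with an AE, although it does not define the link. The patient-level measure named in SAP 5.2 covers the initial escalation day and the escalation visits, 1 + 7 = 8 scheduled clinic days in SAP 6.3, with a check for illness before dosing. So the concern bears mainly on the home, overall and increasing-dose patient-level rows.

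Protocol 2.2 also recognises that nearly all patients have some AE and that dose-level reporting may then be more meaningful; the SAP provides it. The comparison is descriptive, and relatedness is an unblinded judgement in a single-arm trial, whereas all-cause counting works against the hypothesis of fewer AEs. These points limit the severity. They do not supply the missing attributed view.

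**Conclusion.** The gap is confirmed in the SAP text: relatedness is collected for every AE and used in no described analysis. The mock tables (SAP Appendix I) were not available, so a relatedness row there cannot be excluded.

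The size is uncertain. The 34% to 98% over 18 weeks rests entirely on assumed illness rates and pooled terms. It shows that background could be a small or a dominant part of the patient-level result, and that the planned tables would not show which.

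A reader might infer that most children will show a listed AE whatever the product does, or that a true safety gain will be hidden. Neither follows. The first depends on the assumed rate and on pooling separate rows. The second depends on whether the published rates are all-cause or treatment-related, which the documents do not say for these tables; if they are all-cause, the present plan already compares like with like. The point is an inexpensive improvement to interpretation.

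**What to change.** In SAP 11.1 to 11.1.2, keep the all-cause rows of Tables 3.1 to 3.3 and add parallel rows for AEs graded definitely, probably or potentially related. In Table 3.3, state for each published figure whether it is all-cause or treatment-related, and set it against the matching rows from this trial. It would also help to say in SAP 11.1 what links an AE to a dose. If the mock tables already contain such rows, the SAP text should say so.

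The cost is extra table rows from a field already on the case report form, and a check of how each comparator reported its AEs. No new data are needed. The downside is that relatedness is judged unblinded by clinicians who know every child is treated, which is why both views should be shown.

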A commercially developed product, AR101 (Aimmune Therapeutics), an investigational oral biologic drug, was recently trialed in a phase 3 study evaluating efficacy. In the intervention group, 67.2% of patients ages 4–17 tolerated at least a 600-mg dose of peanut protein in the exit food challenge, compared to 4.0% of placebo patients ($p < 0.00001$). In the trial's primary analysis group of ages 4–17, 496 patients from both arms (372 AR101 and 124 placebo) were evaluable for safety. In both arms, the incidence of serious adverse events (SAEs) was low. A total of 10 patients experienced SAEs, none of which were considered life-threatening: nine of these patients were in the AR101 arm (2.4%) and one was in the placebo arm (0.8%). Of the nine AR101 patients who experienced a SAE, five patients experienced mild or moderate SAEs. The other four AR101 patients experienced severe SAEs, which, for two of these patients, were not related to treatment (a concussion and a viral asthmatic exacerbation). Of the two patients who experienced severe SAEs related to treatment, both of whom had elevated baseline peanut-specific IgE levels greater than 100 kU/L, one experienced anaphylaxis, and the other experienced wheezing on the first day of treatment. Both of these patients discontinued from the study. In ages 4–17, 20.4% of AR101 patients and 6.5% of placebo patients discontinued the trial. In the AR101 arm, 12.4% of patients discontinued due to investigator-reported adverse events, including 6.7% due to gastrointestinal adverse events and 2.7% due to systemic allergic hypersensitivity reactions. In the placebo arm, 2.4% of patients discontinued due to investigator-reported adverse events (Table 2).²⁸

Table 2: Discontinuations in the AR101 Group²⁸

	AR101 (n= 372)	
	%	n
Total discontinuations regardless of causality	20.4%	76
Discontinuations not related to adverse events	8.0%	30
Discontinuations related to adverse events	12.4%	46
• Gastrointestinal ²	6.7%	25
• Systemic hypersensitivity reactions ³	2.7%	10
• Respiratory system	1.1%	4
• Cutaneous	0.8%	3
• Other	1.1%	4

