8.3.4 Time Period and Frequency for Event Assessment and Follow-up

The occurrence of an adverse event (AE) or serious adverse event (SAE) may come to the attention of study personnel during study visits and interviews of a study participant presenting for medical care, or upon review by a study monitor.

All AEs including local and systemic reactions not meeting the criteria for SAEs will be captured on the appropriate case report form (CRF). Information to be collected includes event description, time of onset, clinician's assessment of severity, relationship to study product (assessed only by those with the training and authority to make a diagnosis), and time of resolution/stabilization of the event. All AEs occurring while on study must be documented appropriately regardless of relationship. All AEs will be followed to adequate resolution.

Any medical condition that is present at the time that the participant is screened will be considered as baseline and not reported as an AE. However, if the study participant's condition deteriorates at any time during the study, it will be recorded as an AE.

Changes in the severity of an AE will be documented to allow an assessment of the duration of the event at each level of severity to be performed. AEs characterized as intermittent require documentation of onset and duration of each episode.

All reportable events will be recorded with start dates occurring any time after informed consent is obtained until 7 (for non-serious AEs) or 30 days (for SAEs) after the last day of study participation. At each study visit, the investigator will inquire about the occurrence of AE/SAEs since the last visit. Events will be followed for outcome information until resolution or stabilization.

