6.3.3 Assessment of Safety Endpoints

AEs, including Serious Adverse Events (SAEs) will be graded according to severity using the Consortium of Food Allergy Research (CoFAR) scale, which is 5-point ordered scale from mild (1) to death (5). AEs will be categorized by preferred term using the Common Terminology Criteria for Adverse Events (CTCAE) Version 5.0 and for the specific AEs for interest listed in section 5.2, by treatment required, and by study phase (dose escalation study visits, home doses, exit DBPCFC, and overall).

7 Sample Size

We will compare with proportion of patients successfully desensitized as defined by meeting the primary endpoint with the expected placebo rate. The null hypothesis is that the proportion of patients successfully desensitized by boiled peanut oral immunotherapy will not be greater than the expected 20% that has been previously published as the proportion of patients successfully meeting the primary endpoint in OIT studies (which aligns with the expected 20% that would naturally “outgrow” a peanut allergy). If we reject this null hypothesis, we will be able to conclude that the proportion of successfully desensitized by boiled peanut therapy is greater than placebo. The sample of 10 patients will provide >90% power to determine the expected success rate (80%) is greater than a theoretical placebo rate (20%).

8 General Analysis Considerations

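### Patient-level severity rows in SAP 11.1 can overlap, and no row shows how many children had at worst a mild, or at worst a moderate, reaction

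*SAP*

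**What the plan says.** SAP 11.1 assigns each AE to a study phase (the category) and groups it further "by preferred term, CoFAR severity grade, or treatment given". The patient-level analysis takes the number of patients "that experience the AE or SAE at least once will be tabulated", with the rule "Within category and group, each subject will be counted once and any repetitions will be ignored". These counts feed Table 3.1 and the study's column in Table 3.3.

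SAP 11.1.2 carries severity into the descriptive comparison with three published sources: "AEs will be grouped into severity grades, treatments, and preferred terms". It refers to mock Table 3.3 for the comparative data and their sources. No hypothesis test is planned there.

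Protocol 9.1 says the comparison with roasted-peanut OIT covers both how often AEs occur and how severe they are. SAP 6.3.3 grades AEs on the five-level CoFAR scale. Protocol 8.3.4 requires grade changes within an event to be kept: "Changes in the severity of an AE will be documented to allow an assessment of the duration of the event at each level of severity". Neither document says that a patient is to be classified by the worst grade reached.

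**The concern.** Protocol 2.2 expects nearly every child to have some AE during treatment, and daily dosing over months makes repeated reactions likely. If a child is counted in every grade ever experienced, the mild row mostly records that the child reacted at all. The question a reader brings to a severity table is how many children had only mild reactions, how many reached moderate and how many went further. Overlapping rows do not answer it.

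The wording also leaves room for a second reading. If the whole severity classification is one group, each child is counted once, but nothing says at which grade. SAP 13 has biostatisticians produce the tables independently and compare them, so the two programs could follow different readings.

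**Working it through.** The plan states no figure that depends on this rule, so there is none to reproduce. The check compares the two ways of counting.

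**Step 1: can worst grade be recovered from the planned rows?** Take two hypothetical sets of 10 children:

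- Set A: 4 with grade 1 only, 4 with grades 1 and 2, 2 with grades 1, 2 and 3.
- Set B: 2 with grade 1 only, 6 with grades 1 and 2, 2 with grades 1 and 3.

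Counting every grade experienced gives 10/6/2 in both sets (18 entries for 10 children). Counting the worst grade gives 4/4/2 in A and 2/6/2 in B. The planned rows are identical, yet the number with only mild reactions is 4 in one and 2 in the other. Children with nothing worse than moderate could be found by subtraction (10 − 2 = 8) only if the table prints the number with any AE and grade 3 is the highest grade seen. The grade 3 row is 2 under both rules.

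**Step 2: how large is the gap?** Inputs:

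- Doses per child: n = 112 (assumed, 16 weeks of daily doses). The SAP 6.3 schedule puts the exit challenge 18 weeks after Visit 1 and Visit 2 at 1 to 4 weeks after Visit 1, so 14 to 17 weeks, or 98 to 119 days.
- Share of doses with an AE: r. Per-dose rates in Protocol Table 1 run from 0.8% to 46%, and Protocol 2.3.1 cites mild reactions in up to 10–15% of doses.
- Grade split: 80/17/3% for grades 1/2/3 (assumed; the documents give none).
- At most one graded AE per dose, independent across doses (assumed).

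With per-dose probabilities p1, p2, p3 and r = p1 + p2 + p3:

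- At least one AE of grade g: 1 − (1 − pg)^n
- Worst grade 3: 1 − (1 − p3)^n
- Worst grade 2: (1 − p3)^n − (1 − p2 − p3)^n
- Worst grade 1: (1 − p2 − p3)^n − (1 − r)^n

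At r = 5%, p = 0.040, 0.0085, 0.0015:

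- Every grade: 1 − 0.96^112 = 98.97%; 1 − 0.9915^112 = 61.56%; 1 − 0.9985^112 = 15.48%.
- Worst grade: 0.99^112 − 0.95^112 = 0.3244 − 0.0032 = 32.12%; 0.8452 − 0.3244 = 52.08%; 15.48%.

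At r = 0.8%, p = 0.0064, 0.00136, 0.00024:

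- Every grade: 1 − 0.9936^112 = 51.28%; 1 − 0.99864^112 = 14.14%; 1 − 0.99976^112 = 2.65%.
- Worst grade: 0.9984^112 − 0.992^112 = 0.8358 − 0.4067 = 42.91%; 0.9735 − 0.8358 = 13.77%; 2.65%.

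The same formulas across a range (percent of children in grades 1/2/3; sums from unrounded values):

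| Doses with AE | Split | Every grade | Sum | Worst grade | Any AE |
|---|---|---|---|---|---|
| 0.8% | 80/17/3 | 51/14/3 | 68 | 43/14/3 | 59 |
| 2% | 80/17/3 | 84/32/7 | 122 | 53/30/7 | 90 |
| 5% | 80/17/3 | 99/62/15 | 176 | 32/52/15 | 99.7 |
| 10% | 80/17/3 | 100/85/29 | 214 | 10/61/29 | 100 |
| 5% | 90/9/1 | 99/40/5 | 145 | 57/38/5 | 99.7 |

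The difference sits in the mild row: 51.28 − 42.91 = 8.4 points at 0.8% of doses (under one child in 10) and 98.97 − 32.12 = 66.9 points at 5% (nearly seven in 10). The moderate row moves less and the top row not at all. With one AE per child the two rules agree exactly.

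**The case against.** The number of children with at least one event of a given grade is a legitimate statistic, built like the preferred-term rows, which also overlap and need no change. It exceeds the worst-grade count only because it answers a different question. That stands: the planned count is not an error, provided the row says what it is. The mock tables may already carry such a label; their content is not in the available text.

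The consequence is also bounded. The comparison is descriptive, in about 10 children. The rate endpoints in SAP 5.2 (share of subjects with AEs at visits, share of home doses with reactions) do not use grade. At the low end of the published per-dose rates the gap is small. All of this stands.

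Two stronger readings are tempting. A reader might infer that the planned rows are out of line with the published counts, since Protocol 2.2 gives one severity per patient in the AR101 phase 3 trial: "Of the nine AR101 patients who experienced a SAE, five patients experienced mild or moderate SAEs", and the other four severe. The documents do not support that. The split covers only nine patients with SAEs, pools mild with moderate, and would be 5 + 4 = 9 under either rule if each had a single SAE. How the three sources count non-serious AEs by grade is not stated.

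A reader might also infer that the dose-level rows of Table 3.2 overlap in the same way. That depends on whether one reaction to a dose is recorded as one graded AE or as several, which the documents do not settle.

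**Conclusion.** The concern holds in a limited form. On the plain reading of SAP 11.1, the patient-level severity rows of Tables 3.1 and 3.3 can overlap and in general do not show how many children had nothing worse than a mild or a moderate reaction. Severity is part of the stated safety comparison, so that information is worth having, and it can be derived from data already collected.

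The size is conditional. With 112 doses, an 80/17/3% split and independent events, the effect runs from minor at 0.8% of doses to a mild row about three times the worst-grade figure at 5% (99% against 32%). The rate, split and independence are assumptions. The direction is not: rows below the highest grade that occurs are at or above their worst-grade counts, and that highest row is unchanged. The primary endpoint, sample size and power are unaffected.

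No mismatch with published counts is established, and no fault in the dose-level table. This is a nearly free improvement to the tables.

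**What to change.** In SAP 11.1, add patient-level rows to Tables 3.1 and 3.3 that classify each child once, at the maximum CoFAR grade, within each phase and overall. If the per-grade rows are kept, label them as patients with at least one AE of that grade. In Table 3.3, state the counting rule each published source uses, say so where a source does not report it, and set beside each source the study count made the same way. Imposing worst-grade counting on the whole table without knowing the sources' rules could itself misalign the columns.

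The cost is a sentence or two in SAP 11.1, one maximum-per-child step in the programs, a few extra rows, and a check of the three sources. No new data are needed.
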